16.4. CRITERIA FOR DETERMINATION OF MTD

Once all patients enrolled in **Part A** are treated for at least 1 cycle, the study team (see [paragraph 3.2.2.1](#)) determined the MTD to be used in **Part B** based on the safety and tolerability profile of Givinostat observed as well as the PK and PD data, *if applicable*.

16.5. CRITERIA FOR CHARACTERIZATION OF PK

Plasma concentrations from **Parts A** and **B** are evaluated by dose and time point for all patients and time points with at least one PK assessment.

16.6. THE EFFICACY POPULATION

The analysis sets are defined in the [section 5](#).

Patients with a disease-related global deterioration of health status requiring discontinuation of treatment without objective evidence of disease progression at that time should be reported in the electronic CRF as disease progression clinically assessed. Every effort should be made to document the objective progression even after discontinuation of treatment.

The response status of the patient may be reviewed by a panel of independent investigators, *if necessary*.

16.7. SAFETY ASSESSMENTS

Safety and tolerability are evaluated by monitoring haematology and blood chemistry, urinalysis (only in the first cycle of **Part A**), by measurement of physical examination, vital signs, weight, body temperature, ECOG performance status, ECG assessment and evaluation, QTc determination and adverse events recording at scheduled times as described above. Timing information are summarised in the Study flow-chart ([Appendix A](#) of the Study protocol) and detailed in the [paragraph 4.5.4](#) of the

Document: PPD

Author: PPD

Version Number:

V2.2

Version Date:

21 March 2018

Template No: CS_TP_BS016 – Revision 3

Reference: CS_WI_BS005

Effective Date: 01May2012

Copyright © 2012 Quintiles Transnational Corp. All rights reserved.

The contents of this document are confidential and proprietary to Quintiles Transnational Corp. Unauthorized use, disclosure or reproduction is strictly prohibited.

Study protocol.

All significant findings already present during the screening visit before drug administration are reported in the appropriate section of electronic CRF, i.e. Medical History section or Current Medical Conditions section. Significant findings occurring after patient enrolment - identified as AEs - are recorded in Adverse Event section of electronic CRF.

The following criteria are used to assess the safety and tolerability both in **Part A** (primary endpoint) and after 3 and 6 cycles (primary and secondary endpoints, respectively) in **Part B**:

- Number of patients experiencing AEs.
- Type, incidence, and severity of treatment-related adverse events, graded according to Common Terminology Criteria for Adverse Events (CTCAE v. 4.03, 14th June 2010).

16.8. LABORATORY EVALUATIONS

The following laboratory examinations (haematology, blood chemistry and urinalysis) are performed at each investigational unit by a local laboratory co-operating with the Investigator following its own procedures:

- **Haematology:** RBC count, HCT, Hb, MCV, MCH, MCHC, WBC count (full and differential), PLT count;
- **Blood chemistry:** ALT/SGPT, AST/SGOT, ALP, total bilirubin, LDH, creatinine, BUN or Urea (as per site-specific clinical practice), glucose, Na, K, Ca, Cl, Mg, albumin, eGFR determination (according to the Mayo Clinic Quadratic Equation);
- **Urinalysis:** pH, specific gravity, protein, glucose.

The required amount of blood and urine are collected at each visit as scheduled above. Timing information are summarised in the Study flow-chart ([Appendix A](#) of the Study protocol) and detailed in the [paragraph 4.5.4](#) of the Study protocol.

All results of laboratory examinations are entered into the appropriate electronic CRF sections.

16.9. CLINICAL SAFETY ASSESSMENTS

Clinical safety assessments include a thorough physical examination, vital signs assessment

Document: PPD

Author: PPD

Version Number:

V2.2

Version Date:

21 March 2018

Template No: CS_TP_BS016 – Revision 3

Reference: CS_WI_BS005

Effective Date: 01May2012

Copyright © 2012 Quintiles Transnational Corp. All rights reserved.

The contents of this document are confidential and proprietary to Quintiles Transnational Corp. Unauthorized use, disclosure or reproduction is strictly prohibited.

(respiratory rate, pulse rate and sitting blood pressure are measured after 5 minutes of rest), weight, body temperature, ECOG performance status, ECG assessment and evaluation, QTc determination (according to Bazett's correction formula, [Appendix D](#) of the Study protocol).

Of note, if the ECG evaluation demonstrate a prolonged QTc interval (i.e. a QTc interval ≥ 450 msec), two additional ECG evaluations over a brief period of time (i.e. 5 minutes between each recording) are performed. The averaged value of these three ECG evaluations are used for the evaluation of the QTc interval of the related visit. In the electronic CRF all the performed ECG evaluations are entered as well as the average value of multiple ECG evaluation, *if necessary*.

16.10. ADVERSE EVENTS

All AEs either observed by the Investigator, or reported by the patient spontaneously or in a response to a direct question are evaluated by the Investigator and are recorded on the AE section of the electronic CRF.

If the patient discontinues for any reason (including discontinuation for pregnancy), with drug related adverse event ongoing at Study end, he/she will be followed until resolution or stabilization of the event or until it will be reasonable to consider the event not drug related any more or until the start of a new treatment, whichever occurs first.

In case of multiple reasons (e.g. patient withdraws the consent for toxicity), "adverse event" is indicated as the primary reason whenever applicable. All relevant information related to the reason for treatment discontinuation including contributory factors are included on the electronic CRF.

A complete end of Study visit must be performed by 7 days after the last drug intake for any patient permanently discontinuing Study treatment. All drug-related AEs that are still ongoing beyond the last scheduled visit, are followed at subsequent follow-up visits until recovery. If a patient does not return for a scheduled visit, every effort will be made to contact the patient. In any circumstance every effort will be made to complete and report the observations as thoroughly as possible. All relevant information related to the reason for treatment discontinuation including contributory factors are included on the electronic CRF.

For AEs definitions, coding and reporting procedures see [paragraph 5](#) of the Study protocol.

16.11. EXPLORATORY PARAMETERS

EVALUATION OF THE EFFECTS OF GIVINOSTAT ON EACH SINGLE PARAMETER OF THE CLINICO-HAEMATOLOGICAL ELN RESPONSE CRITERIA

Document PPD

Author: PPD

Version Number:

V2.2

Version Date:

21 March 2018

Template No: CS_TP_BS016 – Revision 3

Reference: CS_WI_BS005

Effective Date: 01May2012

Copyright © 2012 Quintiles Transnational Corp. All rights reserved.

The contents of this document are confidential and proprietary to Quintiles Transnational Corp. Unauthorized use, disclosure or reproduction is strictly prohibited.

Each single parameter of the clinico-haematological ELN response criteria [1] (see [paragraph 16.3](#)) is used to evaluate the effect of Givinostat in PV patients.

Only in case the enrolment in **Part A** is slow (i.e. < 5 patients enrolled in 3 months) and the eligibility for this part of the study may be expanded to all patients with cMPN, in this part of the study each single parameter of the ELN and EUMNET criteria can be used to evaluate the effect of Givinostat in ET and MF patients, respectively.

EVALUATION OF THE EFFECTS OF GIVINOSTAT ON PD MARKERS

To evaluate the effects of Givinostat on PD markers, the analysis on mRNA is used.

After evaluation of preliminary results and data exploration, some additional analyses can be performed to identify and quantify other molecular parameters of interest in terms of improving of knowledge of cMPN and the activity of the drug in these disorders.

SPLEEN SIZE ASSESSMENT

The spleen evaluation is performed at the study centre according to the visit schedule outlined in the flow-chart ([Appendix A](#) of the Study protocol).

To evaluate the effects of Givinostat on spleen size, MRI or CT scan is used.

The spleen evaluation is performed during the study according to institutional guidelines and site-specific clinical practice (i.e. MRI or CT scan). For this reason, it is strictly recommended to the sites to provide the Sponsor or their designee with the local normal spleen values of the imaging performed for each patient according to institutional guidelines and site-specific clinical practice (i.e. MRI or CT scan).

The same imaging technique and the same instrument to assess spleen dimension (i.e. MRI or CT scan) is used on a patient throughout the study, *if possible*.

If possible, the spleen dimensions are evaluated as longitudinal diameter (A), antero-posterior diameter (B), transversal diameter (C) and Splenic Volumetric Index (SVI):

$$SVI = (A \times B \times C) / 27$$

IMPROVEMENT OF CONSTITUTIONAL SYMPTOMS

Document: PPD

Author: PPD

Version Number:

V2.2

Version Date:

21 March 2018

Template No: CS_TP_BS016 – Revision 3

Reference: CS_WI_BS005

Effective Date: 01May2012

Copyright © 2012 Quintiles Transnational Corp. All rights reserved.

The contents of this document are confidential and proprietary to Quintiles Transnational Corp. Unauthorized use, disclosure or reproduction is strictly prohibited.

To evaluate the improvement of disease-related constitutional symptoms, the Myeloproliferative Neoplasm Symptom Assessment Form (MPN-SAF) questionnaire (about 20 items) is used in **Parts A and B**, in order to assess the most important clinical symptoms among patients with MPNs [8].

In addition, starting from MPN-SAF questionnaire, in **Part B** also the MPN-SAF Total Symptom Score [9] is assessed as requested by the “new” ELN criteria (i.e. revised ELN response criteria) [2].

REDUCTION OF THE JAK2^{V617F} ALLELE BURDEN

To evaluate the reduction of the JAK2^{V617F} allele burden, the qRT-PCR is used. This molecular examination is performed in a central laboratory (Appendix E of the Study protocol).

After evaluation of preliminary results and data exploration, some additional analyses can be performed to identify and quantify other molecular parameters of interest in terms of improving of knowledge of cMPN and the activity of the drug in these disorders.

REDUCTION OF THE SYMPTOMATIC TREATMENT OF PRURITUS IN TERM OF DOSAGE AND/OR DAYS OF TREATMENT

To evaluate the reduction of the symptomatic treatment of pruritus, the dosage and/or the days of treatment of each concomitant medication taken by the patient to treat this symptom is used. This assessment is performed using the data entered by Investigators in the specific section of the electronic CRF.

EVALUATION OF PRELIMINARY EFFICACY ACCORDING TO THE REVISED ELN CRITERIA

Disease response is evaluated also according to the following “new” ELN criteria (i.e. the revised ELN response criteria) after 6 cycles of treatment with Givinostat in **Part B** [2].

Document: PPD

Author: PPD

Version Number:

V2.2

Version Date:

21 March 2018

Template No: CS_TP_BS016 – Revision 3

Reference: CS_WI_BS005

Effective Date: 01May2012

Copyright © 2012 Quintiles Transnational Corp. All rights reserved.

The contents of this document are confidential and proprietary to Quintiles Transnational Corp. Unauthorized use, disclosure or reproduction is strictly prohibited.

- **Complete remission:**
 1. *Durable* resolution of disease-related signs including palpable hepato-splenomegaly improvement, and *large symptoms improvement*, **and**
 2. *Durable* peripheral blood count remission, defined as HCT < 45% without phlebotomies, and PLT count $\leq 400 \times 10^9/L$, and WBC count < $10 \times 10^9/L$, **and**
 3. No progressive disease, and absence of any haemorrhagic or thrombotic event, **and**
 4. Bone marrow histological remission defined as the presence of age-adjusted normocellularity, and disappearance of tri-linear hyperplasia, and absence of grade > 1 reticulin fibrosis.
- **Partial remission:**
 1. *Durable* resolution of disease-related signs including palpable hepato-splenomegaly, and *large symptoms improvement*, **and**
 2. *Durable* peripheral blood count remission, defined as HCT < 45% without phlebotomies, and PLT count $\leq 400 \times 10^9/L$, and WBC count < $10 \times 10^9/L$, **and**
 3. No progressive disease, and absence of any haemorrhagic or thrombotic event, **and**
 4. No bone marrow histological remission defined as persistence of tri-linear hyperplasia.
- **No response:** any response that does not satisfy partial remission.
- **Progressive Disease:** transformation into post-PV myelofibrosis, myelodysplastic syndrome or acute leukemia (according to the IWG-MRT criteria for the diagnosis of post-PV myelofibrosis and according to WHO criteria for the diagnosis of myelodysplastic syndrome and acute leukemia).

Please note that according to the “new” ELN criteria (i.e. revised ELN response criteria) [2]:

- 1) Molecular response is not required for assignment as Complete Remission or Partial Remission. Molecular response evaluation requires analysis in peripheral blood granulocytes. Complete response is defined as eradication of a pre-existing abnormality. Partial response applies only to patients with at least 20% mutant allele burden at baseline. Partial response is defined as $\geq 50\%$ decrease in allele burden.
- 2) “Durable” is defined as lasting at least 12 weeks.
- 3) “Large symptom improvement” is defined as ≥ 10 points of decrease in MPN-SAF Total Symptom Score [9].

In all cases, the medical judgment of the Investigator’s is taken into account. In particular, if the Investigator’s clinical response assessment – that takes into account the overall medical judgment of the specific patient’s case - is not in agreement with the exact application of the revised clinico-haematological ELN response criteria , the Investigator’s assessment will supersede the “mathematical”

Document: PPD

Author: PPD

Version Number:

V2.2

Version Date:

21 March 2018

Template No: CS_TP_BS016 – Revision 3

Reference: CS_WI_BS005

Effective Date: 01May2012

Copyright © 2012 Quintiles Transnational Corp. All rights reserved.

The contents of this document are confidential and proprietary to Quintiles Transnational Corp. Unauthorized use, disclosure or reproduction is strictly prohibited.

application of these criteria and used for analysis into study report. Also mathematical application of ELN response criteria (not agreed by the medical site team) will be analyzed.

EVALUATION OF THE EFFECTS OF GIVINOSTAT ON EACH SINGLE PARAMETER OF THE REVISED ELN RESPONSE CRITERIA

Each single parameter of the “new” ELN criteria (i.e. revised ELN response criteria) [2] (see [section 16.11.7.](#)) is used to evaluate the effect of Givinostat in PV patients in **Part B**.

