19. EXPLORATORY OUTCOMES

19.1. PARTS A AND B

The following exploratory parameters will be evaluated using ad-hoc descriptive analysis in **Parts A and B** based on ITT analysis set and PP analysis set:

- The effect of Givinostat on each single response parameter according to the clinico-haematological ELN (for PV and ET) [1] and EUMNET response criteria (for MF) [7]; note that only in case the enrolment in Part A is slow (i.e. < 5 patients enrolled in 3 months), the eligibility for this part of the study could be expanded to all patients with cMPN.
- Effects of Givinostat on PD markers.
- Effects of Givinostat on spleen size in patients with confirmed splenomegaly at baseline.
- Improvement of constitutional symptoms evaluated according to MPN-SAF QOL questionnaire [8, 9] including patients without the symptom of headache, pruritus and microvascular symptoms (i.e MPN SAF Score =0) and number and percentage of patient with symptom score from 0 to 3; from 4 to 6 and more than 7.

Document: PPD

Author: PPD

Version Number:

V2.2

Version Date:

21 March 2018

Template No: CS_TP_BS016 – Revision 3

Reference: CS_WI_BS005

Effective Date: 01May2012

Copyright © 2012 Quintiles Transnational Corp. All rights reserved.

The contents of this document are confidential and proprietary to Quintiles Transnational Corp. Unauthorized use, disclosure or reproduction is strictly prohibited.

- Reduction of the JAK2V617F allele burden, tested by quantitative RT-PCR.
- Reduction of the symptomatic treatment of pruritus in term of dosage and/or days of treatment.

The following exploratory parameters will be evaluated using ad-hoc descriptive analysis in Part B based on ITT analysis set and PP analysis set:

- The preliminary efficacy of Givinostat after 6 cycles of treatment according to the “new” ELN criteria (i.e. revised ELN response criteria) [2]. In all cases, the medical judgment of the Investigator’s is taken into account. In particular, if the Investigator’s clinical response assessment – that takes into account the overall medical judgment of the specific patient’s case - is not in agreement with the exact application of the revised clinico-haematological ELN response criteria , the Investigator’s assessment will supersede the “mathematical” application of these criteria and used for analysis into study report. Also mathematical application of ELN response criteria (not agreed by the medical site team) will be analyzed.

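### Item 1 of revised-ELN complete remission contains a stray or conflicting word, so its hepato-splenomegaly requirement is ambiguous and can be read as less strict than the one for partial remission

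*SAP*

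**What the plan says.** The revised ELN criteria are set out in SAP section 16.11, under the evaluation of preliminary efficacy, for Part B after 6 cycles.

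- **Complete remission, item 1:** the line opens with the word 'Durable' and continues "resolution of disease-related signs including palpable hepato-splenomegaly improvement, and" then a large symptom improvement.
- **Partial remission, item 1:** the line opens the same way and continues "resolution of disease-related signs including palpable hepato-splenomegaly, and" then the same symptom element.
- **Items 2 and 3** (blood counts; no progression and no haemorrhagic or thrombotic event) are word for word the same in both categories.
- **Item 4, complete remission:** "Bone marrow histological remission defined as the presence of age-adjusted normocellularity, and disappearance of tri-linear hyperplasia, and absence of grade > 1 reticulin fibrosis".
- **Item 4, partial remission:** "No bone marrow histological remission defined as persistence of tri-linear hyperplasia".
- **No response:** "any response that does not satisfy partial remission".

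The notes below the criteria define 'durable' (at least 12 weeks) and a large symptom improvement (a fall of at least 10 points in the MPN-SAF Total Symptom Score). They do not define improvement of hepato-splenomegaly.

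Where the investigator's assessment and the literal criteria disagree, the investigator's assessment is used. The same section adds: "Also mathematical application of ELN response criteria (not agreed by the medical site team) will be analyzed". Sections 16.11 and 19.1 also call for each single parameter of the revised criteria to be evaluated. Section 19.1 refers to protocol paragraph 4.8.7 for the detailed criteria.

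**The concern.** The layout of the criteria implies that complete and partial remission share items 1 to 3 and differ only in the marrow. One extra word in item 1 breaks that pattern. Resolution of an improvement is not a meaningful criterion, so whoever programs the literal analysis has to choose what the complete-remission line means.

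If the choice falls on improvement, the higher category has the weaker hepato-splenomegaly requirement, with no threshold to apply. Section 20.4 tabulates a spleen volume reduction of at least 35%, but the SAP does not link that figure to item 1. Two programmers could produce different complete remission counts, and different item 1 results, from the same data.

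**Working it through.** The SAP states no figure for this point, so there is none to reproduce. The check compares the two definitions and then classifies patients under each reading.

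**Step 1. Two readings of complete-remission item 1.**

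- Reading A: the leading word 'resolution' governs and 'improvement' is stray. The hepato-splenomegaly requirement is then the same in both categories.
- Reading B: improvement is enough for complete remission. Partial remission still needs resolution.

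**Step 2. Classification.** Assume the symptom element and items 2 and 3 are met. Cross three hepato-splenomegaly outcomes with three marrow outcomes. 'Neither' means that tri-linear hyperplasia has gone but full histological remission is not reached. CR is complete remission, PR is partial remission, and a dash means neither.

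| Hepato-splenomegaly | Marrow | Reading A | Reading B |
|---|---|---|---|
| Resolved | Remission | CR | CR |
| Resolved | Hyperplasia persists | PR | PR |
| Resolved | Neither | – | – |
| Improved only | Remission | – | **CR** |
| Improved only | Hyperplasia persists | – | – |
| Improved only | Neither | – | – |
| Not improved | Remission | – | – |
| Not improved | Hyperplasia persists | – | – |
| Not improved | Neither | – | – |

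One of the nine cells depends on the reading: improved only, with marrow remission. No cell meets both categories under either reading, because item 4 requires marrow remission for one and its absence for the other.

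**Step 3. Size per patient.** A patient in that cell is a complete remission under B and in neither remission category under A. The complete remission rate and the combined remission rate therefore move by the same amount, 1/n.

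- With all 28 planned Part B patients (sections 3.5 and 4): 1/28 = 0.0357, or 3.6 percentage points.
- Section 22 does not count patients who refuse marrow consent for this endpoint, so n can be below 28. If n were 20 (an assumption, for illustration only): 1/20 = 5.0 points.

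The SAP gives no basis for the number of patients in that cell, so no total shift can be stated.

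**Step 4. Single-parameter evaluation.** Item 1 taken alone does not involve the marrow. If it is tabulated with the complete-remission wording, an improved-only patient with the symptom element met counts as meeting it under B and not under A. With the partial-remission wording the patient never counts. The SAP does not say which wording the evaluation uses.

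**The case against.** The strongest case on the other side is that this is an editorial slip in an exploratory definition. Both item 1 lines open with durable resolution, and the extra word could easily have been carried over from the symptom phrase later in the same line. The investigator's assessment supersedes the literal rule, so the literal algorithm feeds only the additional analysis. The endpoint is descriptive, and the full criteria are said to be in protocol paragraph 4.8.7, which was not available for this check. All of this stands. It limits the weight of the point and shapes the fix. It does not remove the point, because the SAP commits to analysing the literal application and each single parameter, and both depend on the exact words.

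A reader might also infer more than the text supports:

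- **That complete remission is easier to reach than partial remission.** It is not. Complete remission also requires full marrow remission. At most one element of item 1 is weaker, and only under reading B.
- **That the wording lets a patient be complete but not partial, so the categories are not nested.** Item 4 makes the categories mutually exclusive by design. Every complete remission fails partial remission whatever item 1 says, and correcting the word would not change that.
- **That every patient whose hepato-splenomegaly improves without resolving is reclassified.** Without marrow remission such a patient is in neither remission category under both readings. A change of category also requires the durable count remission, the symptom fall of at least 10 points, and no progression or haemorrhagic or thrombotic event.

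**Conclusion.** The inconsistency is real and lies in an operative response definition. Complete-remission item 1 is garbled, and one of its two readings sets a weaker hepato-splenomegaly requirement, without a threshold, than partial remission does.

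The consequence is narrow. In the literal revised-ELN analysis, only a patient with improved but unresolved hepato-splenomegaly, full marrow remission and all other items met changes category. Each one moves the rate by 3.6 percentage points on a denominator of 28, and by more on a smaller one. The number of such patients is unknown and may be zero. The item 1 single-parameter evaluation is also open to either reading.

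The primary endpoint uses the earlier ELN criteria in section 16.3, where complete response requires a normal spleen size. The primary response rate and the Simon two-stage decision are therefore unaffected. The conclusion rests on the SAP text alone, and protocol paragraph 4.8.7 may already settle which reading is intended.

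**What to change.** Check both item 1 lines against protocol paragraph 4.8.7. Then delete 'improvement' after 'hepato-splenomegaly' in complete-remission item 1 of SAP section 16.11, so that both categories carry the same item 1: durable resolution, plus the large symptom improvement. The SAP's own structure supports this direction, since both lines already open with durable resolution and items 2 and 3 show that the categories are meant to differ only in the marrow. State that this single wording applies to the literal analysis and to the single-parameter evaluation of item 1.

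The cost is one word in the SAP and a check that the programs match it. The complete remission count may be slightly lower than under the looser reading.
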